1.0 INTRODUCTION

Phyllodes tumors of the breast are uncommon neoplasms which present in young women (median age 45 years). Phyllodes tumors have been characterized by the World Health Organization based on histologic features as benign, borderline or malignant (1,2). Diagnostic histologic features include the number of mitoses per high power field, presence of infiltrating tumor near the margins, and cellularity and degree of stromal atypia. This categorization predicts the tumor's metastatic potential fairly well: in one review 0.4%, 4.3% and 22% of patients with benign, borderline and malignant phyllodes tumors developed metastases (3).

According to recent SEER data, approximately 500 women are diagnosed with malignant phyllodes tumors in the US each year and about half of those patients are treated with breast conserving resections as the only therapy (4). We reviewed the literature to determine the rate of local recurrence after margin-negative breast conserving resection of borderline malignant and malignant phyllodes tumors (5). A total of 13 studies were identified. Local recurrences occurred in 37/124 (21%) patients. Twelve of fifty (24%) patients with borderline malignant tumors and 25/124 (20%) patients with malignant phyllodes tumors experienced a local recurrence. The median follow-up in these studies ranged from 3.1- 9 years. Of note, the vast majority of recurrences occurred within 2 years of surgery: the median time to recurrence was 24 months or less in all but one of these studies.

This local recurrence rate is unacceptably high, as there are multiple adverse consequences of in-breast recurrences. There is substantial psychological morbidity. There is cosmetic morbidity: patients with recurrent phyllodes tumors will require wide local re-excision or mastectomy. Furthermore, several studies have shown that local recurrence of phyllodes tumors is a strong predictor of metastatic spread (6-8). A multivariate analysis in one of these studies indicated that local recurrence of phyllodes tumors was associated with a significantly increased risk of death (8). Concern remains for the potential for local recurrences to metastasize, as was demonstrated in a recent meta-analysis of randomized prospective studies of patients with invasive breast cancer (9). In this study it was determined that for every 4 local recurrences that were avoided, one breast cancer death was prevented.

In 1998 we initiated a prospective single arm study (DMS 9801) to determine whether adjuvant radiation therapy after breast conserving resection of borderline and malignant

phyllodes tumors decreases the local recurrence rate (5). Forty six women were treated at 30 different institutions. The mean patient age was 49 years (18-76). Thirty patients (65%) had malignant phyllodes tumors, the rest were borderline malignant. The mean tumor diameter was 3.7 cm (0.8-11 cm). Eighteen patients had a negative margin on the first excision. The median size of the negative margin was 0.35 cm (range <0.1-2 cm). Twenty eight patients underwent a re-excision because of positive margins in the initial resection. Two patients died of metastatic phyllodes tumors. With a median follow-up of 56 months (range 12-129 months), none of the 46 patients developed a local recurrence (local recurrence rate zero (95% CI 0 - 8%)). We concluded that adjuvant radiation therapy decreased the local recurrence rate after breast conserving resections of phyllodes tumors.

A recent retrospective report from the Rare Cancer Network also provides strong support for the use of adjuvant radiation therapy after resection of phyllodes tumors (4). Of 159 patients with borderline or malignant phyllodes tumors, 109 were treated with breast conserving surgery and 50 underwent mastectomy. Thirty six received adjuvant radiation therapy. When all 159 patients were considered the percentage free of local recurrence at 10 years in the group that received radiation therapy was significantly better than the group that did not receive radiation therapy (86% vs 59%, p= 0.02). Of the 109 patients treated with breast conserving surgery, 11 underwent radiation therapy and 68% were free of local recurrence at 10 years compared to 54% of the 98 patients who underwent lumpectomy without radiation therapy. Of the 50 mastectomy patients, 25 underwent radiation therapy and 92% were free of local recurrence at 10 years, compared to 78% of the patients undergoing mastectomy without radiation therapy. While the trends in each of these subgroups favor radiation therapy, the differences were not statistically significant. In multivariate analysis the only favorable independent prognostic factor was the use of radiation therapy.

On the basis of the foregoing studies we have recommend adjuvant radiation therapy for all patients with malignant phyllodes tumors who undergo breast conserving resections. We feel that adjuvant radiation therapy is also indicated after breast conserving resection of patients with borderline malignant phyllodes tumors. Although the concern for the metastatic potential of a locally recurrent borderline phyllodes tumor is less than that for a locally recurrent malignant phyllodes tumor, borderline phyllodes tumors do metastasize in 2-4% of cases (3,4). Furthermore, it is well documented that recurrent phyllodes tumors can progress to a more malignant phenotype than that seen in the initial tumor (9-13). Finally, since borderline

malignant phyllodes tumors locally recur as frequently as malignant phyllodes tumors after margin negative resection, adjuvant radiation therapy can prevent the morbidity associated with the need for additional surgery in 20-25% of these patients.

New methods for delivering breast radiotherapy are being developed that allow radiation to be delivered solely to the area of the surgical resection site, termed partial breast radiation. The main advantage of partial breast radiation is that it simplifies treatment for the patient: radiation is delivered twice a day for 5 days, rather than 5 days per week for 6 weeks. The main concern is that partial breast irradiation might miss other sites of breast cancer in the ipsilateral breast. This is a significant concern for patients with invasive ductal or lobular carcinoma, where multicentric tumors may be present in 5 to 10% of patients. This concern was lessened by data from the NSABP-06 study, where patients were randomized to receive lumpectomy or lumpectomy plus radiation therapy. In this study the development of tumors "elsewhere" in the ipsilateral breast (away from the primary tumor site) was the same (3%) whether or not the patient received adjuvant radiation therapy (14). Indeed, evidence is accumulating from prospective studies that adjuvant partial breast irradiation after resection of invasive adenocarcinoma of the breast results in rates of local recurrence that are comparable to those seen after whole breast radiation therapy. The study with the longest follow-up utilized several brachytherapy catheters to radiate just the area around the surgical resection site in 120 patients undergoing breast conserving surgery (15). The local recurrence rate at 5 years was 1%, which is comparable to that achieved in patients undergoing whole breast radiation. The Mammosite® catheter has simplified the delivery of partial breast radiotherapy. This is a balloon catheter which can be easily inserted in the cavity left after breast conserving surgery. A radioactive source is placed in the center of the balloon to deliver radiation. A large registry of 1440 patients treated with partial breast radiation indicates that at 3 years of follow-up the local recurrence rate after breast conserving surgery and Mammosite® brachytherapy is very low: 1.6% (16). An alternative method of partial breast radiotherapy which is gaining in popularity is external beam partial breast radiation therapy. This technique does not require placement of a balloon catheter in the breast, but relies on careful dosimetry to focus external beam radiation to the area around the surgical site. Although there is only short follow-up data available for patients treated with external beam PBI, this technique has been used for greater than 70% of women treated with PBI on the NSABP B-39 protocol. Both Mammosite® and external beam partial breast radiation

therapy are currently being compared to whole breast radiation therapy in the prospective randomized study, NSABP-B39.

In contrast to patients with invasive carcinomas of the breast, it is very rare for patients to have multicentric phyllodes tumors. In our literature review all 37 recurrences seen in the 124 patients that had undergone margin negative breast conserving resections were at the site of the initial tumor resection. Therefore we hypothesize that adjuvant partial breast irradiation is likely to be as effective as whole breast radiation therapy after resection of malignant phyllodes tumors.

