8.0 STATISTICAL CONSIDERATIONS

The primary objective of this study is to evaluate the in-breast recurrence rate of borderline and malignant phyllodes tumors treated with breast conserving resection and adjuvant partial breast radiation therapy. Based on our literature review, the in-breast recurrence rate after margin negative breast conserving resection alone is approximately 21 percent. A clinically meaningful improvement for the experimental therapy would be an in-breast recurrence rate of 5 percent or less.

The secondary objective is to compare the local recurrence rate observed after partial breast radiation therapy with that observed in historical controls treated with whole breast radiation therapy after breast conserving resection with negative margins (study DMS 9801, ref 5). This recurrence rate was zero (0/46 patients).

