8.1 Statistical analysis

The rate of in-breast recurrence will be calculated with an exact binomial confidence interval. A binomial test (i.e., one sample proportion test) will be used to compare this rate to the rate of 21% determined from the literature for margin negative breast conserving resection alone. To address the secondary aim the rate from this study will be compared to the rate (0/46) obtained in the study using adjuvant whole breast radiation using a Fisher's exact test.

Additional analysis will include descriptive summaries of adverse events, time to recurrence and survival. Time to recurrence and survival will be estimated separately for the borderline and malignant tumor groups using the product limit method.

Sample Size and Power Considerations

A total sample of 50 patients will be enrolled and followed for recurrence. This yields sufficient power (i.e., 80%) to detect that adjuvant partial breast radiation is better than margin negative breast conserving resection alone, if indeed this adjuvant therapy reduces the rate to 6% or less, and the rate with resection alone is 21%. This calculation sets the type I error rate (α) at the usual 0.05. The 95% exact binomial confidence interval has an expected range of 1% to 15% if the actual rate is 5% (whereas it is 0% to 8% if the actual rate is 1%, and it is 4% to 22% if the actual rate is 10%). In comparison to the adjuvant whole breast radiation in which our prior study found no in-breast recurrences in 46 women, partial breast radiation will be identified as having a significantly higher rate if its actual rate is 15% or higher (assuming an α =0.5, and use of a Fisher exact test).

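### Does the misprinted fraction 37/124, which is 30%, undermine the 21% null rate of the primary test?

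*Combined protocol and SAP*

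**What the plan says.** The Introduction (section 1.0) summarises 13 studies of margin-negative breast-conserving resection alone. It states the overall result as "Local recurrences occurred in 37/124 (21%) patients" and then splits it by grade: "Twelve of fifty (24%) patients with borderline malignant tumors and 25/124 (20%) patients with malignant phyllodes tumors experienced a local recurrence". Near its end, when arguing that recurrences arise at the resection site, it refers to "all 37 recurrences seen in the 124 patients that had undergone margin negative breast conserving resections".

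Section 8.0 carries the percentage forward: "the in-breast recurrence rate after margin negative breast conserving resection alone is approximately 21 percent". Section 8.1 makes it the comparator of the primary one-sample binomial test, which is to "compare this rate to the rate of 21% determined from the literature for margin negative breast conserving resection alone". It also bases the sample size on it: 50 patients, 80% power if the true rate is 6% or less against 21%, and a type I error of 0.05 with no statement of one or two sides.

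**The concern.** The printed fraction and the printed percentage disagree: 37/124 is about 30%. The 124 is used for the whole reviewed population in two separate places, so a stray keystroke in a single sentence does not explain it. The fraction is also the only derivation the protocol offers for its null rate.

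If the fraction were right and the percentage wrong, the trial would be testing against the wrong benchmark. A result of 5 to 8 recurrences in 50 would be significant against 29.8% but not against 21% (two-sided exact test), so the answer to the primary question could turn on which figure is correct.

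**Working it through.** **Inputs.** From the Introduction: 37 recurrences overall, 12/50 borderline, 25/124 malignant, and the printed percentages 21%, 24% and 20%. From section 8.1: n = 50, null 21%, alternative 6%, α = 0.05.

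**Step 1: the printed fractions.**
- Overall as printed: 37/124 = 29.8%. This does not match 21%.
- Borderline: 12/50 = 24.0%. Matches.
- Malignant: 25/124 = 20.2%. Matches.

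**Step 2: rebuild the total from its parts.**
- Numerators: 12 + 25 = 37, the printed overall count.
- Denominators: 50 + 124 = 174.
- Pooled rate: 37/174 = 21.3%, which rounds to the printed 21%. The exact 95% interval is 15.4% to 28.1%.

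**Step 3: could 124 be the true total?**
- A pooled proportion must lie between its subgroup proportions, here 20.2% and 24.0%. A value of 29.8% lies outside them.
- If 124 were the total, the malignant group would number 124 − 50 = 74, and 25/74 = 33.8%, not the printed 20%.
- Working back from the percentage, 37/0.21 = 176. Whole-number denominators that round to 21% run from 173 (37/173 = 21.4%) to 180 (37/180 = 20.6%). The sum 174 is in that range and 124 is far outside it.

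**Step 4: does correcting the denominator change the test?** Let X be the number of recurrences in 50 patients. The cutoff c is the largest value with P(X ≤ c | null) ≤ 0.025 for a two-sided test, or ≤ 0.05 for a one-sided test. Power is P(X ≤ c | 6%).

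| Null rate | Two-sided cutoff (lower tail) | Power at 6% | One-sided cutoff (lower tail) | Power at 6% |
|---|---|---|---|---|
| 21% | ≤ 4 (0.012) | 82.1% | ≤ 5 (0.034) | 92.2% |
| 37/174 = 21.3% | ≤ 4 (0.011) | 82.1% | ≤ 5 (0.031) | 92.2% |
| 37/124 = 29.8% | ≤ 8 (0.019) | 99.7% | ≤ 9 (0.042) | 99.9% |

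The first two rows have the same cutoffs and the same power. The plan's claim of 80% power at 6% or less is supported on the two-sided reading: power is 82.1% at 6% and still 80.3% at a true rate of 6.2%. The third row applies only to a null that the plan never uses and that step 3 rules out.

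**Step 5: the second appearance of 124.** The argument there is that every recurrence was at the original site. That is 37 of 37 whether the cohort numbered 124 or 174.

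**The case for a change.** The strongest case for acting is that the benchmark is the foundation of a single-arm trial and its printed source is wrong twice. In the second place no subgroup counts stand nearby to expose the slip. The literature table itself is not in the documents, so the reading of 174 is an inference. If 124 did prove to be the total, the null, cutoff and power would all need to be redone.

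The misprint is real, and a glance at the source review before anyone cites the fraction is sensible. The rest carries little weight. Taking 124 as the total requires the overall 21%, the malignant denominator and the malignant 20% all to be wrong, together with the 21% in sections 8.0 and 8.1. It would also contradict the Introduction's statement that borderline tumors recur locally as often as malignant ones, since the rates would then be 24% and 34%. Taking 174 as the total requires one number, repeated once, to be wrong.

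It could also be argued that the plan should print its rejection cutoff and an interval for the benchmark. The cutoff depends on whether the test is one- or two-sided (5 or 4), which section 8.1 leaves open. That is a separate matter, and correcting a denominator would not settle it. An interval around the literature rate would be informative but would alter no planned result.

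**Conclusion.** The fraction is misprinted; the rate is not. The malignant-only denominator was used as the pooled total in two sentences of the Introduction, and the adjacent subgroup counts recover 37/174 = 21.3%, in agreement with the 21% used in sections 8.0 and 8.1. The protocol offers one null rate, not two: 30% is stated nowhere and cannot arise from subgroups of 24% and 20%.

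Correcting the denominator moves the exact cutoff by 0 events and the power at 6% by 0 percentage points, whether the test is one- or two-sided, and leaves the sample size of 50 as it is. An analyst following section 8.1 tests against 21% and reaches the same conclusion either way. The slip is clerical and no change to the plan follows. This rests on the printed subgroup counts being correct, which their own percentages bear out; the underlying literature table was not available to check.

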2.0 OBJECTIVES

- 2.1 The primary objective is to determine the local recurrence rate for patients with borderline or malignant phyllodes tumors treated with breast conserving resection with negative margins and adjuvant partial breast radiation therapy.
- 2.2 The secondary objective is to compare the local recurrence rate observed after partial breast radiation therapy with that observed in historical controls treated with whole breast radiation therapy after breast conserving resection with negative margins (study DMS 9801, ref 5).
- 2.3 Additional secondary objectives will be to observe the incidence of tumor development elsewhere in the breast and the rate of distant metastases.

3.0 PATIENT SELECTION

3.1 Eligibility Criteria

3.11 Histologic proof of phyllodes tumor of borderline or malignant grade, as first defined by Pietruszka and modified by Azzopardi and adopted by the World Health Organization (1,2,17):

Borderline malignant: 5-9 mitoses/10 HPF, pushing or infiltrating margins, 2+ (moderate) stromal cellularity and atypia.

Malignant: 10 or more mitoses / 10 HPF, predominantly infiltrating margins, usually 3+ (severe) stromal cellularity and atypia but occasionally 2+.

- 3.12 The tumor has been excised with a breast-conserving resection and there is no tumor seen at any of the margins of the resection.
- 3.13 No prior breast carcinoma or ductal carcinoma in situ in the ipsilateral breast. Patients with a local recurrence of a previously excised phyllodes tumor are eligible if the recurrence is in the area of the previous excision.
 - 3.14. No history of irradiation of the ipsilateral breast.
- 3.15 No evidence of other areas worrisome for cancer on physical examination and mammography of the ipsilateral breast.
 - 3.16 Age \geq 18 years.
 - 3.17 Informed consent
 - 3.18 Documentation that either: 1) the patient's medical insurance company has certified that they will pay for the cost of radiation therapy treatments, or 2) a letter from the patient indicating that they explicitly understand the costs of radiation therapy and that the sponsor (Principal Investigator) of this study will not be held responsible for these costs.

3.2 Exclusion Criteria.

- 3.21 Histologically positive margins.
- 3.22 Breast carcinoma or ductal carcinoma in situ in the ipsilateral breast.
- 3.23 A history of irradiation to the ipsilateral breast.
- 3.24 Pregnancy. A urine pregnancy test will be performed on each fertile premenopausal female prior to entry into the study. Patients with childbearing potential must employ effective contraception during the radiation therapy.
- 3.25 A radiation planning CT scan which demonstrates a target lumpectomy cavity that is not clearly delineated or a target lumpectomy cavity/whole breast reference volume > 30%.

3.26 Unacceptable radiation therapy quality assurance parameters, as defined in Section 5.

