4.2 Pretreatment data to be submitted

Patient name

Patient birth date and age at diagnosis

History, noting presence or absence of prior breast surgery, irradiation and breast malignancies

Location of tumor in the breast and side affected (left/right)

Operative report from the tumor excision

Pathology report from the tumor excision, with information on margins and tumor size, as described in section 4.1

Bilateral mammogram report

Ultrasound report, if obtained

MRI report, if obtained.

Referring physician, surgeon, radiation oncologist and treating institution

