5.0 RADIATION THERAPY

Radiation therapy will be administered in the vicinity of the center where the surgical resection was performed. Adjuvant radiation must start within 12 weeks of breast excision or reexcision. External beam partial breast radiation will be administered per guidelines used in the NSABP B-39/RTOG 0413 protocol.

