7.0 DATA COLLECTION AND SAFETY MONITORING

Pre-therapy evaluation data, as detailed above, radiation therapy treatment data, as well as the results of post-therapy exams and imaging studies will be collected by the Office of Clinical Research at DHMC, and reviewed quarterly by the Principal Investigator ([name]). The NCCC Safety and Data Monitoring Committee will also monitor this protocol on a quarterly basis.

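### Section 3.24 states no pregnancy safeguard between study entry and the first fraction: the test is tied to entry, and contraception is required only during the radiation course

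*Combined protocol and SAP*

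**What the plan says.** Section 3.24 lists pregnancy, without qualification, as an exclusion. It then adds two provisions. The first is on testing: "A urine pregnancy test will be performed on each fertile premenopausal female prior to entry into the study". The second is on contraception: "Patients with childbearing potential must employ effective contraception during the radiation therapy".

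The timing of treatment is set elsewhere. Sections 5.0 and 5.1.4 allow radiation to start up to 12 weeks after excision or re-excision. Section 5.1.4 requires completion within 10 days of the first fraction, and section 5.3.2.1 gives 10 treatments over 5 to 10 days.

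Two other exclusions bear on when entry can be settled. Section 3.25 excludes on imaging grounds, including "A radiation planning CT scan which demonstrates a target lumpectomy cavity that is not clearly delineated" (it also limits the ratio of cavity to breast volume). Section 3.26 excludes for "Unacceptable radiation therapy quality assurance parameters, as defined in Section 5". The available text does not define the point of study entry in relation to either.

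**The concern.** The protocol treats pregnancy as a reason not to irradiate, and it asks for both a test and contraception to that end. The two measures do not meet in time. The test looks back from entry, while the contraception duty begins only with treatment. Between entry and the first fraction neither applies.

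What is at stake is the safety of a small number of patients: an unrecognised early pregnancy could be exposed to partial breast irradiation without any departure from the protocol. The population makes this possible. Section 3.16 admits patients from age 18, section 1.0 gives a median age of 45 at presentation, and 3.24 itself anticipates fertile premenopausal patients. These facts show that such patients are expected, not how many there will be.

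**Working it through.** There is no stated figure to reproduce, and no sample size or error rate is involved. The check sets the timing rules side by side and asks which of them applies to a conception in each interval.

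1. **Between the pregnancy test and entry.** The exclusion applies, because the patient is pregnant at entry and 3.24 is not limited to pregnancies shown by a test. What may fail is detection: 3.24 sets no maximum age for the test, so a test done early in screening complies and could miss a later conception.

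2. **Between entry and the first fraction.** The entry exclusion has already been applied. The entry test is past and no repeat is required. The contraception sentence has not yet taken effect. Section 5.1.6 lists what is done before the first treatment, and it is imaging only. The pretreatment data in 4.2 and the plan criteria in 5.1.7 and 5.3.2.1 do not mention pregnancy. No stated rule applies.

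3. **During the course.** The contraception requirement applies.

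The duration of required contraception follows directly:

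- during treatment: 5 to 10 days (5.3.2.1);
- before the first fraction: 0 days (3.24).

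An outer limit for the second interval can be given. Section 3.12 requires that the tumor has already been excised with clear margins, so entry cannot precede the qualifying resection. Radiation must start within 12 weeks of excision or re-excision, and 12 × 7 = 84 days. The interval from entry to first fraction therefore lies between 0 and 84 days.

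This is a ceiling, not an estimate. Margin assessment, central slide review for grade (4.1), the planning CT (3.25) and plan quality assurance (3.26) all take up part of the 84 days. If they are finished before entry, as their place among the eligibility requirements suggests, what remains before the first fraction is probably short. The documents do not give its length.

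**The case against.** The strongest reply is that 3.24 already does most of the work. Pregnancy is excluded outright, testing is mandatory and contraception is mandatory during exposure. Eligibility under 3.25 and 3.26 cannot be settled until planning is done, so the uncovered interval is likely to be brief. This stands, and it is why the point is limited to conception after entry and graded as minor. It does not close the gap, since no section fixes when entry occurs or limits the time from entry to treatment.

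A second reply is that the rule may exist elsewhere. Consent pages and a stretch of text between 3.26 and 4.1 were not available for this review. Section 5.0 also defers to the NSABP B-39/RTOG 0413 guidelines, which are not supplied. This stands too: the conclusion is about the text that could be read. Nor does the protocol prevent a site from advising contraception earlier or repeating the test.

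A reader might draw two stronger conclusions. One is that any conception between the test and the first fraction is unregulated. The documents do not support that, because a woman pregnant at entry is excluded whatever the date of her test.

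The other is that the coordinating office could not detect an old or missing test. Section 7.0 collects "Pre-therapy evaluation data, as detailed above, radiation therapy treatment data", and none of the items in 4.2 is a pregnancy test; the nearest is "History, noting presence or absence of prior breast surgery, irradiation and breast malignancies". Treatment is local, since "Radiation therapy will be administered in the vicinity of the center where the surgical resection was performed", and of the earlier study whose accrual method is reused, section 1.0 reports that "Forty six women were treated at 30 different institutions". But 4.2 is not an eligibility checklist. It also omits informed consent (3.17), the insurance or cost documentation that 3.18 expressly requires, and the cavity ratio in 3.25. Section 8.2 says separately that required information goes to the principal investigator or a co-investigator. Absence from 4.2 therefore does not show that the test goes unchecked, and the number of institutions in the earlier study says nothing about pregnancy testing in this one.

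**Conclusion.** The concern holds in a narrow form. In the available text, a conception after entry and before the first fraction is covered by no stated rule, and such a patient could be irradiated with 3.24 met as written. Between test and entry the weakness is one of detection, because the age of the test is not limited.

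The gap is probably short. The number of fertile premenopausal women among the 50 planned patients and the expected number of pregnancies cannot be derived from the documents, and no estimate is offered. The conclusion assumes that no further rule stands in the consent form, in the B-39 guidelines or in text not available here. It is a cheap improvement of optional severity. The primary endpoint, the sample size and the analysis are unaffected.

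**What to change.** Amend 3.24 in two respects.

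- Require effective contraception from the date of the pregnancy test through the last fraction. This is the main change: it covers the whole interval however long it turns out to be, including any time between test and entry.
- Require a negative urine test shortly before the first fraction, for example within 7 days. The 7 days are an assumed window, which the sponsor should set; it should be counted back from the first fraction and not from entry. The entry test serves if it falls within the window and is repeated only if it is older.

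The cost is a wording change and an occasional repeat urine test. A repeat is more likely where the treating physician lacks RTOG approval and the plan must be approved before treatment (5.3.2) than where no prior submission is needed (5.3.1).
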